4.1.2 Secondary endpoints

The pre-defined secondary endpoints include:

The pre-defined secondary endpoints include:

- 1. Pregnancy loss < 10 weeks gestation
- 2. Pregnancy loss > 10th week of gestation of a morphologically normal fetus documented by ultrasound or by direct examination of the fetus
- 3. Premature birth of a morphologically normal neonate < 34 weeks due to any of: pre-eclampsia, eclampsia, recognized features of placental insufficiency.
- 4. Gestational age at delivery
- 5. Birth weight
- 6. Delivery by Caesarean section
- 7. Apgar score < 7 at 5 min
- 8. Neonatal morbidity (bleeding or thrombotic complications, infections, congenital abnormalities)
- 9. Days to hospital discharge following delivery (mother & child)
- 10. Thrombotic events in the mother during pregnancy and 6 weeks post-partum.
- 11. Days of neonate in special care
- 12. Safety and tolerability of hydroxychloroquine in the mother and in the neonate

4.2 Trial Design

This is a double blind randomized controlled trial (RCT) of women with aPL planning to fall pregnant, who will be randomized to hydroxychloroquine or an identically looking placebo in addition to their usual medication.

According to our sample size we will enroll 328 pregnant women. In order to achieve this number of patients we will randomize 400 patients.

Our hypothesis is that hydroxychloroquine improves aPL-related pregnancy complications.

The HYPATIA trial has been designed as a multicenter RCT. Participating centers in the UK include Guy's and St Thomas' NHS Foundation Trust, University College London NHS Foundation Trust; the Royal Free London Hospitals, Liverpool Women's Hospital NHS Foundation Trust; Manchester University Hospital, Oxford University Hospital and Cambridge University Hospitals.

In the EU participating centres include: Copenhagen, Hvidovre, Odense, Århus, Ålborg, Sønderborg (all in Denmark), University Hospital Torino/Italy; and Dublin University Hospital/Ireland, Calgary University Hospital/Canada. The HYPATIA trial is supported by an accredited Clinical Trials Unit (King's College London Clinical Trials Unit).

Each center runs a dedicated pregnancy clinic following a routine care protocol for pregnant women with aPL. The patients are closely monitored during their pregnancy and are followed up at least once every trimester, if needed more closely. A visit assessment schedule is outlined in on page 16. The study procedures for the HYPATIA trial are outlined specifically and are almost identical with the standard of care for these patients. We expect all participating sites to follow these study procedures. Data from the routine clinical visits prior to study entry may be used in the HYPATIA study. This includes data from standard of care samples, such as blood results (full blood count, biochemistry, liver profile, auto-antibody status (i.e. Lupus anticoagulant, anti-cardiolipin antibodies, anti- β 2-glycoprotein-I, ENA antibodies).

For women entering this trial additional hospital visits are therefore not required, as trial visits will coincide with the standard of care visits. Women who decide to participate in the HYPATIA trial will have their usual medication, with hydroxychloroquine or placebo as additional therapy. Women will have a routine blood test assessing full blood count, kidney and liver function and a physical exam (including heart and lung stethoscopy) every 3 months before becoming pregnant and once every trimester. This blood test will coincide with their usual follow-up/study visit and women do therefore not need to attend more often.

Only for women in selected centres: Women attending selected centres will be invited:

- To donate blood samples in order to assess 1. biomarkers and 2. the pharmacokinetics of hydroxychloroquine in pregnancy.

[figure not shown]
These data will be analyzed separately from separate funding sources and do not form part of HYPATIA trial.

Centre	Country	HYPATIA study only	Option for research bloods
Rigshospitalet	Denmark	х	Х
Hvidovre	Denmark	x*	
Odense	Denmark	х	Х
Århus	Denmark	х	Х
Ålborg	Denmark	х	Х
Sønderborg	Denmark	X*	
GSTT, London	UK	х	Х
Royal Free, London	UK	х	
UCLH, London	UK	х	
Royal Free, London	UK	х	
Oxford	UK	х	
Cambridge	UK	х	
Liverpool	UK	х	
Manchester	UK	х	
Turin	Italy	х	Х
Dublin	Ireland	х	Х
Calgary	Canada	х	Х
*sites only screen fo	r eligibilty (l	out no randomisation)	

An overview of the selected centres is given below:

The trial will be carried out in accordance with the protocol and current statutory requirements/legislation.

4.3 Trial Flowchart

HYPATIA trial study procedures

	Pre-pregnancy		Pregnancy			Post- partum	
	Screening visit*	Baseline visit*	Pre- pregnancy visits §	1st Trimester	2nd Trimester	3rd Trimester	Post- partum visit†
Written informed consent	x	-					
Demographics	x						
Eligibilty assessment (1)	x	x					
Past medical history (2)	x						
Smoking history	x				x		
Past pregnancy history (3)	x						
Current medication	x	x	x	x	x	x	x
Height	x	~	~	~	~	~	~
Weight	x						
- · · · · · · · · · · · · · · · · · · ·							
Collection of blood results (4)	X						
Blood pressure & Pulse	X						
Urine dip	X						
Randomisation		X					
Dispensation IMP		X	X	X	X	X	
Adverse events monitoring		X	X	X	X	X	X
Physical exam (incl stetoscopy)	X		X	x	X	X	
Blood sample (5)	X		X	X	X	X	
Info about current pregnancy (6)			~	X	X	X	
Compliance check (7) Blood for additional research (8)		×	X	x x	X	x	x
Growth scans		X	X	*	x x	x	X
Uterine Artery Doppler (20-24 weeks)					x (9)	^	^
Child gender					× (9)		x
Birth date							x
Child APGAR at 5 min							x
Days of admission (mother&child)							x
Gestational age							x
Mode of delivery (Cesarean Y/N)							x
Birth weight							x
Neonatal morbidity (neonatal bleeding or thrombotic complications, infections, congenital abnormalities, days in neonatal special care)							x
* These visits can all be completed on the same	day. Consen	t within 3 mo	onths.				
§ Visits every 3 months until patient pregnant, th max 4 times (a total of 12 months)	en new dispe	nsation of s	tudy drug and	dispensation	every 3 mor	nths. Pre-preg	nancy visits
† Follow up visit should be completed within 6 we can contact the participant to obtain the study inf		atient is una	ble to attend c	linic within th	e timeframe	of 6 weeks, tl	ne study team
(1) Eligibility assessment: persistent presence of	aPL twice 12	2 weeks apa	rt, ENA negati	ve			
(2) Past medical history as per exclusion criteria other significant past medical history. Blood sam antibodies. Blood results can be obtained from re screening as per standard of care.	nple review (F	BC, kindne	y and liver pro	file) and resu	Its will be co	llected: aPL a	ntibodies, ENA
 (3) Past pregnancy history - to record in chronolo premature birth < 34 due to pre-eclampsia, eclar 						s, miscarriag	e > 10 weeks,
(4) max 12 months old (antiphospholipid antibod	ies (aPL) type	e and titres i	incl local cut of	f, ENA antibo	odies). Repe	at aPL if need	led.
(5) blood sample include full blood count, kidney and liver function as standard of care. For the screening bloods, in case any results are available and are less than 3 months old they can be used.							
(6) IVF pregnancy (Y/N), singleton/twin or triplet pregnancy, current gestation, estimated date of delivery							
(7) Compliance check (Kit number to be noted, d	ate of curren	t kit started	& ended, numl	ber of tablets	taken, numl	per of tablets	missed)
(8) Only for patients in selected centres: optional	research blo	ods					
(9) Data can be collected on 2nd or 3rd Trimeste	r visit. All sca	ans should b	e recorded on	eCRF.			

5 Trial Medication

5.1 Investigational Medicinal Product (IMP)

1. Active hydroxychloroquine description:

The active is hydroxychloroquine 200mg film coated tablets. The tablet is presented a white, circular, biconvex film coated tablet debossed with '200' on one side and plain on the other side (Quinoric®, MA holder: Bristol Laboratories Ltd (tablets PL 17907/0017). A list of excipients can be found in the Summary of Product Characteristics (SmPC).

The active product is deblistered from blister packs, packed, labelled, and UK QP released and distributed to Great Britain (GB) study sites by Guy's and St Thomas' NHS Foundation Trust, Pharmacy Manufacturing Unit (MIA IMP: 11387).

2. Placebo **description**: The placebo is a white, circular, biconvex tablet debossed with '200' on one side and plain on the other side to match theappearance of Hydroxychloroquine 200mg film-coated tablets, PL 17907/0017. The Simplified Investigational Medicinal Product Dossier (sIMPD) details the composition of the placebo.

The placebo product is manufactured, packed, labelled, and UK QP released and distributed to Great Britain (GB) study sites by Guy's and St Thomas' NHS Foundation Trust, Pharmacy Manufacturing Unit (MIA IMP: 11387).

The Sponsor has contracted with Sharp Clinical Services to provide EU import and EU QP release, as well as distribution of the IMP to EU study sites. These activities will be performed by Manufacturing Packaging Farmaca (MPF) B.V., Heerenveen, The Netherlands (Manufacturers Authorisation: 108630F) on behalf of Sharp Clinical. An additional agreement for IMP shipment will be made for Calgary in Canada.

The Kings Clinical Trials Unit (KCTU) Intervention Management System will be used to allocate blinded supplies to patients. The study team, site pharmacy team and patient will remain blind to the treatment allocation.

The KCTU trials pharmacist will be unblinded and will have access to the KCTU Intervention Management System to maintain IMP stock levels, both centrally and at study sites. This individual will be responsible for placing orders for delivery to study sites.

Packaging and labelling:

The active and placebo tablets will be packed into Annex13-labelled, high-density polyethylene (HDPE), tamper-evident, child-resistant closure bottles. Each treatment pack will contain 96 tablets and will have a unique treatment pack number.

Multi-language labels will be applied to the bottles, allowing the IMP to be shipped to any recruiting site globally. The Sponsor will be responsible for approving the label content in each country.

Once randomized, a unique pack number in the trial arm that the participant has been randomized to, will be automatically allocated in the KCTU Randomization and Intervention Management system. A copy of the randomisation notification will be emailed to all individuals that have been given access to receive these details. A study specific prescription will be sent to the dispensing pharmacy, along with a printed copy of the randomization email. At each subsequent visit, study site staff will access the KCTU Randomization and Intervention Management system and allocate a new unique pack number for the participant. Study site pharmacists must cross check the prescription and the randomization notificationat each dispensing episode to ensure the correct pack number is dispensed. Study medication will be dispensed at randomization and quarterly thereafter until month 9 or until pregnancy is confirmed. Once pregnancy is confirmed, a new pack is dispensed. During pregnancy study medication will continue to be dispensed on 3-monthly basis until pregnancy end.

In exceptional circumstances (such as lockdown during Covid19 pandemic), the dispensedIMP can be sentto the participant by post and the participant will not have the physical exam or blood tests at that time but will have the routine clinical exam and blood test at the subsequent study visit.

5.2 Dosing Regimen

Patients will be randomised to either hydroxychloroquine 200 mg once daily or an identical placebo, which is to be taken in addition to the participants usual medication. Hydroxychloroquine should ideally be taken with a meal or a glass of milk.

The duration will include the time span from entering the trial to time of conception and length of pregnancy.

The maximum pre-pregnancy treatment period is 12 months in case a woman does not achieve pregnancy in this time.

Therefore, the maximum duration of treatment for a participant can be 21 months (7 dispensing visits) including the length of pregnancy. Refer to list of study visits below:

- Pre-pregnancy Randomisation (baseline visit)
- Pre-pregnancy Month 3
- Pre-pregnancy Month 6
- Pre-pregnancy Month 9
- Pregnancy Trimester 1
- Pregnancy Trimester 2
- Pregnancy Trimester 3

5.3 IMP Risks

Hydroxychloroquine is traditionally an antimalarial drug and since the 1950's has been widely used in the treatment of patients with rheumatoid arthritis or systemic lupus erythematosus (SLE). Hydroxychloroquine treatment of pregnant patients with SLE was first described more than three decades ago and its safety during pregnancy has been extensively documented and systematically reviewed [5-7].

The European Medicines Agency has licensed hydroxychloroquine as orphan medical product for the treatment of APS (EU/3/16/1820). We are aware that hydroxychloroquine is labelled as 'contraindicated in pregnancy' according to the SmPC. However, it is widely used in women during pregnancy and lactation and is recommended for the use in pregnancy by European and British Societies (the European League against Rheumatism (EULAR) and the British Society for Rheumatology (BSR)).

[name] is a member of the BSR working group on 'prescribing antirheumatic drugs in pregnancy'. Their guidance has been published in *Rheumatology* [9, 44]. After reviewing more than 810 pregnancies in the literature where women were prescribed hydroxychloroquine through pregnancy, they recommended that hydroxychloroquine is the antimalarial drug of choice in pregnant patients with autoimmune diseases and they did not identify significant risks for intrauterine exposure to the fetus. According to these NICE approved BSR guidelines, hydroxychloroquine is the antimalarial of choice for pregnant patients requiring immune modulation [9, 44]. The BSR guideline has been updated in November 2022, as hydroxychloroquine is still the antimalarial of choice for pregnant women and deemed safe before conception, during pregnancy and also during breastfeeding [45, 46]. Safety assessments for mother or baby are not recommended.

Further supporting the safety of hydroxychloroquine in pregnancy and lactation, the EULAR have very recently published their European recommendations on the use of hydroxychloroquine in pregnancy and lactation. The EULAR group highlighted that hydroxychloroquine is safe in pregnancy and that there is no evidence of an increased risk of malformations in children exposed to hydroxychloroquine, that hydroxychloroquine can be continued throughout pregnancy and during breastfeeding [47].

Use of hydroxychloroquine in patients with psoriasis and porphyria may precipitate a severe attack. These patients are therefore excluded from the HYPATIA study. Retinal toxicity has been described with high dose hydroxychloroquine, however, low doses of hydroxychloroquine (less than 6.5mg/kg bodyweight) are very rarely associated with retinopathies. Patients participating in the HYPATIA trial will be receiving hydroxychloroquine 200 mg once daily, which is half of the maintenance dose according to the SmPC, or an identical placebo. For a patient weighing 75 kg, a daily dose of 200 mg is equivalent 2.6 mg/kg body weight and this dose has been shown not to be associated with retinal toxicity [48-50]. Women with a body weight less than 45 kg are not eligible for the trial

What is known about the dosing of HCQ in pregnancy:

According to the SmPC a dose of 200 mg hydroxychloroquine is the low maintenance dose for the indication of rheumatoid arthritis, discoid and systemic lupus erythematosus.

Several hundred pregnancies exposed to hydroxychloroquine 200 to 400 mg daily during the first trimester did not find an increase in congenital malformations including cardiac conduction disturbances in children exposed antenatally to hydroxychloroquine as reported by Ostensen et al in 2006 [9, 51]. The BSR working

group on the use of antirheumatics in pregnancy, of which [name] is a member, identified an additional 23 studies; 2 systematic reviews [52, 53], 2 case controls [54, 55], 10 cohort [56-65], 3 case series [66-68] and 6 case reports [69-74] providing further information on 810 pregnancy exposures to 200 – 400 mg HCQ. The BSR working group has in November 2022 updated their guideline, and still recommends that HCQ is safe in pregnancy.

In two more recent retrospective clinical studies of HCQ in patients with obstetric APS, patients were also exposed to a dose of 200mg – 400mg hydroxychloroquine daily and no adverse events in the neonates were reported [41, 42].

When reviewing the literature on the use of 200 mg daily, several studies have focused on possible long-term effects of HCQ in children exposed in utero or during lactation (in one study the average daily maternal dose of hydroxychloroquine was 317 mg and in the second study and in the second study the daily dose was 200 mg) [75, 76]. No decrease in visual acuity, visual field or colour vision, changes in electroretinogram and electro-oculogram were detected in a series of six children studied during the first year of life and up to 4 years of age [77]. A case-control study including 133 pregnancies exposed to hydroxychloroquine found no visual, hearing, growth or developmental abnormalities in children followed up for 108 months. Electrocardiograms of exposed children were normal [51, 78].

What is known about the pharmacokinetics of hydroxychloroquine in pregnancy:

Hydroxychloroquine is a diastereoisomer, has basic properties and is given as the sulphate. While being relatively well absorbed orally and with good bioavailability, hydroxychloroquine has a long and variable plasma terminal elimination half-life (approximately 40-60 days). Hydroxychloroquine undergoes renal clearance [79]. HCQ passes across the placenta, with cord blood concentrations nearly identical to those found in maternal blood, suggesting that during pregnancy the level of exposure to HCQ in mother and fetus is similar[80]. A systematic review including a meta-analysis of hydroxychloroquine exposed pregnant patients with autoimmune diseases including five studies did not show any increased risk of congenital malformations in babies born to mothers who were exposed to hydroxychloroquine in pregnancy[53]. These findings are in line with the more recent systematic review of anti-rheumatics in pregnancies published by Flint et al[9, 44]. To the best of our knowledge no studies exist to inform on the plasma levels of patients exposed to hydroxychloroquine during pregnancy.

Length of hydroxychloroquine exposure:

The maximum length of hydroxychloroquine exposure for women participating in the HYPATIA study is 12 months + the individual pregnancy length, i.e. a maximum total length of 21 months hydroxychloroquine exposure.

The main concern associated with hydroxychloroquine exposure is the development of retinopathy[81]. A number of retrospective and prospective studies have attempted to assess the risk of developing HCQ retinopathy and to identify risk factors for toxicity[48, 82]:

In the largest study to date, Wolfe and Marmor screened 3995 patients who had received HCQ for SLE or RA for self-reported toxicity, followed by specialist confirmation of these cases. In this study definite or probable HCQ toxicity was noted in 0.65% (95% CI: 0.31, 0.93%). They reported a clear increased risk with duration of exposure: <0.3% for those with HCQ exposure of less than 5 years but up to 2% for those with exposure of 10 to 15 years. Interestingly, they found no association with

daily dosage, but they note that their data regarding this was incomplete[82]. Levy's retrospective chart review of 1207 patients receiving HCQ found no cases of definite toxicity in patients on HCQ <6.5 mg/kg/day, but one patient with definite toxicity and five with indeterminate but probable toxicity in those who received >6.5 mg/kg/day HCQ[48]; the patient with definite toxicity had taken HCQ for 7.3 years at a dose of 6.98 mg/kg/day. Overall probable toxicity occurred in 0.5% of patients in the Levy series, a similar proportion to the Wolfe study.

Smaller studies include those of Mackenzie[83], who found no cases of HCQ retinopathy in a cohort of >900 patients with rheumatoid arthritis on HCQ and Wang's study[84], which reported one patient with HCQ retinopathy in 156 patients with SLE who had taken HCQ, and that patient had previously taken HCQ for 6 years at a dose 6.5 mg/kg/day[84].

In a more recent retrospective study on 2361 patients, the prevalence of hydroxychloroquine related retinopathy was estimated higher at 7.5% and depending on dose and duration of therapy can increase to 20-50 % after 20 years of therapy using more sensitive testing methods[85].

Prospective studies however support a low rate of HCQ toxicity. Mavrikakis and colleagues reported on their prospective series of 526 patients who received HCQ, of which 400 patients had received at least 6 years of treatment. Prior to 6 years of treatment, no patients had developed retinopathy. Two patients subsequently developed retinopathy (one at 6.5 years and one at 8 years), equating to a rate of 0.5% for those patients with over 6 years of treatment. The mean duration of treatment in this group was 8.7 years, indicating a relative paucity of patients with longer follow-up[86].

Accurately estimating the incidence of HCQ retinopathy is challenging. Most studies are case series or retrospective cohorts, and the relatively few prospective studies are limited in size and duration of follow-up. The data available does, however, suggest that HCQ retinopathy remains rare especially if patients are treated with doses less than 5 mg/kg and less than 5 years. In our HYPATIA study women will be maximally exposed for 21 months in total and as we are excluding women weighing less than 45 kg (200 mg once daily in a patient weighing 45 kg equals 4,4 mg/kg).

Other data on adverse effects in relation to exposure length are limited. To the best of our knowledge the only study assessing exposure length in relation to toxicity towards the myocardium is published by Costedoat-Chalumeau et al, who in a series of 85 patients with connective tissue disease evaluated heart conduction disorders with electrocardiograms (ECG). Patients were exposed between 12 months up to 50 months, and the group could not show any significant difference between cases and controls[87].

The Royal College of Ophthalmologists (RCOphth) guideline published in 2018 recommended to conduct a baseline eye exam (incl. visual fields test and optical coherence tomography) in patients who start HCQ therapy and in whom it was planned to continue treatment for at least 5 years. However, these 2018 guidelines have been updated in December 2020 (REF), and **baseline retinal monitoring is no longer** recommended. The advice on baseline monitoring has been reviewed on the basis of a large UK audit of 782 individuals who had taken hydroxychloroquine for less than five years. It found that none had an abnormality on testing that would have meant stopping treatment. The guidelines also point out that a significant proportion of those who start taking hydroxychloroquine are no longer prescribed it five years later.

Patients with a known or newly diagnosed retinopathy will not be included into the study, and women will be therefore asked at study entry if they have any new visual problems. Those with visual problems will be referred to a formal eye exam. We also

exclude patients with renal insufficiency (renal replacement therapy) as this may lead to in increased plasma levels of hydroxychloroquine. We are also aware the SmPC states that hydroxychloroquine has been associated with cardiomyopathy, and that caution has to be taken in patients with severe neurological or blood disorders. Patients in the HYPATIA trial will be monitored with physical examinations and blood tests to ensure their safety. All trial teams are aware of the possible side-effects and in case patients describe symptoms that may be related to hydroxychloroquine side-effects these will be investigated accordingly.

As hydroxychloroquine may precipitate a porphyria attacks and worsen psoriasis, these patients will therefore be excluded from the HYPATIA study. We will advise patients, that hydroxychloroquine may alter the need for glycaemic control in those with diabetes.

The table indicates hydroxychloroquine's potential side-effects according to the SmPC. We will ensure all participants safety and use the following modalities to screen and monitor any potential side-effects:

Side-effects according to SmPC	Frequency according to SmPC	Modality to monitor/screen
Retinopathy	Uncommon	 Pt with retinopathy will not be included as per exclusion criteria, and women will therefore be asked if they experience any visual problems prior to study entry (if this is the case they will be sent to a formal eye test)
Cardiac effects (cardiac failure)	Uncommon	- Regular heart and lung stethoscopy
Hepatic or renal illness	Unknown	 Pts with known hepatitis or renal failure will not be entered into the study Liver and renal function will be monitored every three months Pts in whom renal function deteriorates (i.e. creatinine clearance of less than 30 ml/min) will be withdrawn from the trial
Severe gastrointestinal, neurological or blood disorders	Unknown	 Pts with severe gastrointestinal, neurological or blood disorders will not be entered into the study
Glucose-6-phosphate dehydrogenase (G6PD) deficiency	Unknown	 Pts with G6PD deficiency will not be entered into the study and those of Mediterranean origin or a family history will be screened as per standard of care
Bone marrow depression	Rare	 Regular full blood count (includes red and white blood cells and thrombocytes)
Hypoglycaemia	Unknown	 Pt with diabetes on antidiabetics will be made aware of this side-effect and we will ask women to communicate this to their diabetes care givers
Musculoskeletal effects (patients on	Unknown	 Physical exam of muscle strength (shoulder and hip girdle)

long-term treatment according to SmPC)		
Dermatological reactions (Steven Johnson syndrome and toxic epidermal necrolysis)	Unknown	 Pt will be made aware of these side-effects (mentioned in "Patient info sheet') and will be asked if they have experienced any skin rashes. Pts will be informed to stop treatment in case of progressive skin rash with blisters)
Hereditary problems of galactose intolerance, the lactase deficiency or glucose-galactose malabsorption	Unknown	 Pts with galactose intolerance, the lactase deficiency or glucose-galactose malabsorption will not be entered into the study
Ototoxicity in the newborn	Limited data	 All babies will undergo the usual exam as part of the NHS routine care. No extra exam is recommended.
Retinal toxicity in the newborn	Limited data	- No extra exam is recommended.

Newborn screen for potential retinal and oto-toxicity:

In babies exposed to potentially retino or ototoxic drugs, we were initially asked to perform a direct ophthalmoscopy and a diagnostic Auditory Brainstem Response (ABR) test at 4kHz – a high frequency sound along with diagnostic transient-Evoked otoacoustic emissions (TEOAE) which are objective tests more sensitive than the newborn hearing screen.

However, all major updated guidelines from societies relevant to the field have been updated since our first protocol proposal in 2017. The societies including the British Society for Rheumatology from 2022 (BSR), the British Society for Ophthalmology 2021, the American College of Rheumatology 2020 (ACR) and The European Alliance of Associations for Rheumatology formerly the European League Against Rheumatism 2017 (EULAR) recommend no baby eye or ear screening [10, 45, 46, 88, 89].

As a direct ophthalmoscopy and ARB and a TEOAE are exams that take time, and requires the babies to comply with the exam technique (the baby needs to sleep for the hearing test), and none of the babies born of mothers participating in the study as of November 2022 have had abnormal hearing eye tests, we therefore exclude the eye and ear screen of the babies born to mothers participating in the HYPATIA study from the current protocol version 10.0.

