6.2 Exclusion Criteria

- 1. Women who are already pregnant
- 2. Allergy or adverse event to hydroxychloroquine. Hypersensitivity to the active substance, 4-aminoquinoline or any of the compounds of the IMP or placebo.
- 3. Current treatment with hydroxychloroquine
- 4. Age < 18 or > 45
- 5. Body weight < 45 kg
- 6. Psoriasis
- 7. Uncontrolled epilepsy
- 8. Anti-Ro antibodies
- 9. Renal replacement therapy
- 10. Other severe active co-morbidities (HIV, hepatitis B, severe gastrointestinal, neurological or blood disorders)
- 11. Porphyria

- 12. History of retinopathy or newly diagnosed retinopathy
- 13. History of galactose intolerance, lactase deficiency or glucose-galactose malabsorption
- 14. History of glucose-6-dehydrogenase deficiency
- 15. Participation in any other IMP trial at the time of consent
- 16. Previous pregnancy failure on hydroxychloroquine

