6.3 Selection of Participants

Definitions used in the HYPATIA study:

- Screening: Time from consent to randomisation
- Baseline visit: Randomisation to treatment arm/Initial IMP dispensation
- Pre-pregnancy study visits: Visits between randomisation and achieved pregnancy
- Pregnancy study visits: Study visits on routine follow up visits

Potentially eligible women will be identified in routine outpatient clinics. Patients will receive full information about the HYPATIA study, and if they decide to take part written informed consent will be obtained. Patients will have as much time as they need to consider their participation. Eligibility will be assessed and provided all eligibility criteria are fulfilled, study randomization can be undertaken and the IMP can be dispensed (baseline visit) (see trial flow chart).

Once a woman is enrolled into the HYPATIA study, she will attend follow up visits every three months until she falls pregnant (at 3, 6, 9 and 12 months, defined as prepregnancy visits) in addition to her usual standard pregnancy care.

If no pregnancy is achieved in the 12 months from entering the study, this will be recorded in the study CRF and the study medication will be stopped. Once a woman has been enrolled into the HYPATIA study and has started taking the IMP, she will have a blood test including full blood count, kidney function and liver function every three months during the pre-pregnancy period and during pregnancy (these tests will coincide with her follow up visits) and are to ensure that it is safe to take the IMP (hydroxychloroquine).

On these visits the IMP will be repeatedly dispensed and compliance will be assessed. This will be documented in medical records and recorded in the eCRF.

When a woman falls pregnant she will contact the study team and will attend her first pregnancy visit (1st trimester visit). At this visit a new trial medication will be dispensed.

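### Section 5.3 bars entry for known hepatitis, but exclusion criterion 10 admits mild or inactive non-B hepatitis; separately, the renal stopping rule removes women from the trial, not just from study drug

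*Protocol*

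**What the plan says.** **Hepatitis.** Section 5.3 tabulates hydroxychloroquine side-effects and how each will be screened for or monitored. The row on hepatic or renal illness says: "Pts with known hepatitis or renal failure will not be entered into the study". Criterion 10 in 6.2, repeated in the synopsis, excludes "Other severe active co-morbidities (HIV, hepatitis B, severe gastrointestinal, neurological or blood disorders". Section 6.3 says: "Eligibility will be assessed and provided all eligibility criteria are fulfilled, study randomization can be undertaken and the IMP can be dispensed". Footnote 2 of the flowchart in 4.3 describes the screening history as "Past medical history as per exclusion criteria other significant past medical history". Section 4.2 adds a general statement: "The trial will be carried out in accordance with the protocol".

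**Renal entry.** The prose before the 5.3 table says the trial will "exclude patients with renal insufficiency (renal replacement therapy) as this may lead to in increased plasma levels of hydroxychloroquine". Criterion 9 in 6.2 reads "Renal replacement therapy". The pharmacokinetics text in 5.3 notes: "Hydroxychloroquine undergoes renal clearance".

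**Renal stopping.** The same 5.3 row removes from the trial any woman whose creatinine clearance falls below 30 ml/min. Sections 6.5 and 7.2 repeat the rule; they give the level as 30 ml/min without saying below. Elsewhere, 6.5 lets the investigator take a woman off study drug and asks women who come off treatment to stay in follow-up. It ends data collection when a woman herself chooses to leave the study. The missing-data framework in 10.1 aims to follow up everyone randomised, including those who stop allocated treatment.

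**The concern.** The protocol gives two entry rules for the same condition and does not say which prevails. A site that applies 5.3 would turn away a woman with, say, inactive hepatitis C or quiescent autoimmune hepatitis; a site that applies 6.2 would randomise her. The safeguard that 5.3 presents as protecting the liver is then not fully carried into the criteria checked at randomisation.

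The renal rule matters for a different reason. The protocol distinguishes stopping study drug from leaving the study, and its main analysis follows intention to treat. A safety rule phrased as leaving the trial invites a site to stop collecting outcomes. New-onset renal insufficiency is one of the protocol's own features of pre-eclampsia (8.2), and birth before 34 weeks because of pre-eclampsia is a component of the primary endpoint. Outcomes in such women are ones the analysis would want to keep.

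**Working it through.** No design figure of the trial is in question, so the check is a comparison of texts.

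**1. Each entry bar in the 5.3 table against 6.2.**
- Retinopathy: criterion 12.
- Severe gastrointestinal, neurological or blood disorders: criterion 10.
- G6PD deficiency: criterion 14.
- Galactose intolerance and related conditions: criterion 13.
- Renal failure: criterion 9, because the prose before the table glosses the renal exclusion as renal replacement therapy.
- Known hepatitis: matched only in part, by hepatitis B in criterion 10.

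Hepatitis is the one bar without a full counterpart.

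**2. Two readings of criterion 10.**
- If the bracketed list is closed, hepatitis B is the only hepatitis excluded.
- If it gives examples, other hepatitis is excluded only when severe and active.
- On both readings, known mild or inactive non-B hepatitis passes 6.2 and fails 5.3.

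**3. Any other liver criterion.** None appears in 6.1, 6.2 or the synopsis. Liver function is reviewed at screening (7.1), but no value excludes a woman.

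**4. Which text operates.** Section 6.3 ties randomisation to the eligibility criteria, so in practice 6.2 decides.

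**5. Renal stopping rule.**
- 5.3, 6.5 and 7.2: the woman leaves the trial.
- 6.5, on treatment: a woman may come off study drug and is asked to stay in follow-up.
- 10.1: follow-up is to be attempted in everyone randomised, whatever happens to treatment.

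Taken literally, the first conflicts with the third. The second shows that the protocol already has the right category for a safety stop.

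**6. Scale.** The document gives no prevalence of mild or inactive non-B hepatitis. As an assumption only, 0.25% to 2% of the 400 women to be randomised:
- 400 × 0.0025 = 1
- 400 × 0.005 = 2
- 400 × 0.01 = 4
- 400 × 0.02 = 8

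The range has no source in the protocol, and the true number could be zero.

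**The case against.** The best defence on hepatitis is that 6.2 is plainly the operative list: it is numbered, repeated in the synopsis and tied to randomisation by 6.3, while the 5.3 table summarises safety monitoring. The general statement in 4.2 about following the protocol does not turn 5.3 into a rival eligibility list. Screening also takes in other significant history and a liver profile, and liver function is rechecked every three months, so known hepatitis would probably come to light. Most of this stands and keeps the point minor. It does not remove the mismatch: the table states a flat bar on entry, and detecting hepatitis is not the same as having a rule for it.

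A reader might infer three stronger things that the document does not support.

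- *That the renal failure bar in 5.3 also contradicts criterion 9.* The prose in 5.3 defines the renal exclusion as renal replacement therapy, which is criterion 9.
- *That admitting a woman already below 30 ml/min is a contradiction.* Nothing requires an entry limit to equal a stopping limit. Aligning them is sensible, given renal clearance and the protocol's stated worry about raised drug levels, but it is a suggestion.
- *That the renal stopping rule will lose endpoint data.* The sentence in 6.5 that ends data collection concerns a woman's own decision to leave. The same section follows adverse events whatever the treatment status, and 10.1 asks for continued follow-up. The stopping level also differs from the creatinine criterion for pre-eclampsia (above 90 umol/L), and 6.5 and 7.2 expect it to be reached rarely. Loss of data is a risk from loose wording, not a consequence the protocol lays down.

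**Conclusion.** The point holds as a minor internal inconsistency. Known mild or inactive non-B hepatitis is barred in 5.3 and admitted by 6.2, and this does not depend on how criterion 10 is read. The wording of the renal stopping rule is a separate small fault: read literally, it is at odds with the follow-up required in 10.1.

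Few women are likely to be affected. The illustrative 1 to 8 rests entirely on an assumed prevalence. Both arms are screened under the same rules, so the hepatitis mismatch gives no reason to expect a biased comparison, and no effect on power or on the treatment estimate is claimed for either point. The case for acting is that entry rules and safety text should agree and that the renal correction protects intention-to-treat data at almost no cost.

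**What to change.** 1. **Hepatitis.** Make 5.3 and criterion 10 agree. Since 5.3 states the bar as a safety measure, the default is to add known hepatitis to criterion 10 in 6.2 and the synopsis. The clinicians should decide whether long-resolved disease is meant to count. If the narrower rule is intended, change the 5.3 row to match criterion 10 instead; that is one line.
2. **Renal stopping rule.** In 5.3, 6.5 and 7.2, replace the wording with *withdrawn from study drug, with follow-up continued*, and state the level as below 30 ml/min in all three places.
3. **Optional.** Add *or creatinine clearance below 30 ml/min* to criterion 9 in 6.2 and the synopsis.

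The cost is amendment wording. Item 3 also needs one clearance calculation at screening from bloods already required, with no new sample or visit. Its small downside is that a few women may be excluded; widening criterion 10 could likewise exclude a few.
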